7.2. Tirzepatide for Chronic Weight Management

Tirzepatide is a glucose-dependent insulinotropic polypeptide (GIP) receptor and glucagon-like peptide-1 (GLP-1) receptor agonist (GLP-1 RA).¹ Tirzepatide lowers body weight with greater fat mass loss than lean mass loss. Tirzepatide decreases calorie intake, and the effects are likely mediated by affecting appetite. Tirzepatide is a once-weekly subcutaneous injection. Tirzepatide is based on the GIP sequence and contains aminoisobutyric acid (AiB) in positions 2 and 13, a C-terminal amide, and Lys residue at position 20 that is attached to 1,20-eicosanedioic acid via a linker. The empirical formula is C₂₂₅H₃₄₈N₄₈O₆₈.¹

Tirzepatide is approved as an adjunct to a reduced-calorie diet and increased physical activity for chronic weight management in adults with an initial body mass index (BMI) of 30 kg/m² or greater (obesity), or 27 kg/m² or greater (overweight) in the presence of at least one weight-related comorbid condition (e.g., hypertension, dyslipidemia, type 2 diabetes mellitus, obstructive sleep apnea, or cardiovascular disease).

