9.7. Variables

9.7.1. Exposure Definitions and Ascertainment

Exposure to tirzepatide is a condition for inclusion into the exposed cohort. Exposure is defined as bodily uptake of any dose of tirzepatide at any time during pregnancy (from conception to pregnancy outcome) or prior to pregnancy (within a specified time based on the product's half-life). Due to the half-life of tirzepatide (approximately 5 days), tirzepatide is likely to be eliminated from the body within 5 half-lives (25 days or 3.5 weeks). Therefore, individuals exposed to tirzepatide within ≤ 25 days of DOC will be considered exposed. Individuals in the tirzepatide cohort who are exposed to other GLP-1 RA therapies during pregnancy or within 5 times the half-life of the drug prior to conception will be excluded from the main analysis to prevent class effect interactions. However, they may still be enrolled into the study as part of the tirzepatide exposed cohort.

Exposure to comparator products for weight management is defined as bodily uptake of any dose of a qualifying product for weight management at any time during pregnancy (from conception to pregnancy outcome) or prior to pregnancy (within 5-half-lives of DOC). Detailed information on drugs for weight management and their respective exposure windows are detailed in Drugs of Interest for Cohort Eligibility.

Detailed information on dose, route, frequency, dates/duration of exposure, and indication/reason for use will be collected, and exposure will be further categorized by earliest trimester of exposure. Section 9.7.5 provides information on the methods used to determine gestational age and trimester of exposure.

Exposure information will be updated at each pregnancy follow-up and changing exposures will be accounted for in the analysis. For example, if a pregnant individual was enrolled into the comparator cohort but later during pregnancy became exposed to tirzepatide, for the analysis they would be included in the tirzepatide exposed cohort.

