9.11.2. Statistical Methods

Registry data will be summarized in tables and listings by study cohort, as appropriate. These data include maternal demographic characteristics and pre-pregnancy anthropometrics, pregnancy information, maternal obstetrical history, family history of congenital malformations, disease information, maternal exposures during pregnancy, pregnancy outcome information (including gestational age of outcome), and infant outcome information.

For each continuous variable, the number of observations, median, mean, standard deviation, minimum, and maximum will be reported. For each categorical variable, the frequency and percentage in each category will be reported. The frequency and percentage of participants with missing data for each data point will be presented. Results will be rounded to one decimal place; therefore, percentages may not always add up to 100.

Pair-wise comparisons of demographic and baseline characteristics and event rates of the outcomes of interest will be conducted between the study cohorts, as follows:

- Comparison #1: Tirzepatide exposed cohort vs. AOM active comparator cohort

- Comparison #2: Tirzepatide exposed cohort* vs. AOM unexposed comparator cohort
*Comparison #2 will include a subset of tirzepatide exposed cohort who have obesity or are overweight with at least one weight-related comorbid condition at the time of conception so as to improve comparability to AOM unexposed comparator cohort with the same obesity-related eligibility criteria.

For the analysis, participants from all countries will be pooled. Comparisons will be conducted using the methods described below, and p-values and 95% confidence intervals will be reported, as appropriate, to reflect statistical uncertainty. All outcomes will be analyzed as binary variables. The study is not powered for multiple comparisons; thus, p-values associated with secondary or exploratory outcomes will be nominal.

In addition, the prevalence of the outcomes in the general population and/or populations of individuals overweight or with obesity, from the literature, will be used to put the registry-observed outcome prevalences into context.

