9.11.2.2. Analysis of Secondary and Exploratory Outcomes

Prevalence of the secondary and exploratory outcomes will be calculated according to the conventions described in [Table 9.7](#). In general, the prevalence of each outcome will be calculated by dividing the number of cases of the outcome by the appropriate denominator for that particular outcome, based on clinical knowledge.

Table 9.7. Calculation of Secondary and Exploratory Outcome Prevalence

Outcome [Exposure window]	Numerator	Denominator
Secondary outcomes		
Maternal pregnancy complications		
Gestational diabetes [Exposure: Any trimester]	Individuals with gestational diabetes	Individuals included in the analysis population
Sensitivity analysis: Gestational diabetes	Gestational diabetes among pregnancies with pregnancy outcome data	Individuals with pregnancy outcome data
Pregnancy-induced hypertension [Exposure: Any trimester]	Individuals with pregnancy-induced hypertension	Individuals with pregnancy of 20 gestational weeks or more
Sensitivity analysis: Pregnancy-induced hypertension	Pregnancy-induced hypertension among pregnancies with pregnancy outcome data	Individuals with pregnancy of 20 gestational weeks or more with pregnancy outcome data
Pre-eclampsia [Exposure: Any trimester]	Individuals with pre-eclampsia	Individuals with pregnancy of 20 gestational weeks or more
Sensitivity analysis: Pre-eclampsia	Pre-eclampsia among individuals with pregnancy outcome data	Individuals with pregnancy of 20 gestational weeks or more and with pregnancy outcome data
Eclampsia [Exposure: Any trimester]	Individuals with eclampsia	Individuals with pregnancy of 20 gestational weeks or more
Sensitivity analysis: Eclampsia	Eclampsia among individuals with pregnancy outcome data	Individuals with pregnancy of 20 gestational weeks or more with pregnancy outcome data
Fetal Outcomes		
SAB [Exposure: DOC to $\leq 19^{6/7}$ gestational weeks]	SABs among individuals with pregnancy outcome data who are enrolled (and exposed, if applicable) prior to 20 gestational weeks	Individuals with pregnancy outcome data who are enrolled (and exposed, if applicable) prior to 20 gestational weeks
Induced abortion [Exposure: Any trimester]	Individuals with pregnancy ending in induced abortions	Individuals included in the analysis population
Sensitivity analysis: Induced abortion	Induced abortions among individuals with pregnancy outcome data	Individuals with pregnancy outcome data

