- For SAB and preterm birth, prevalence will be calculated among the subset of individuals who are enrolled in the registry prior to 20 and 37 gestational weeks, respectively. Additionally, for these time-to-event outcomes, data will be censored at appropriate time points: 20 gestational weeks for SAB and 37 gestational weeks for preterm birth.
- For pregnancy complications prevalence will be calculated according to the following assessment windows:
 - Pregnancy induced hypertension reported for the first time among participants after 20 weeks gestation.
 - Pre-eclampsia/eclampsia reported among participants after 20 weeks of gestation.
 - New-onset gestational diabetes reported among participants at any time during pregnancy
 - Inadequate maternal weight gain reported among participants at any time during pregnancy.
 - HG reported among participants anytime during pregnancy.
- Prevalence will be calculated at multiple time points for postnatal growth deficiency, rapid infant weight gain, and infant developmental delay will be assessed at 4 months (± 2 weeks) and 12 months (± 2 weeks) of infant age. At each time point, prevalence will be calculated among infants with data available for the particular outcome at that time point. If there is no assessment available at 4 and/or 12 months, available data will be evaluated based on the actual time of assessment (e.g., if the infant was measured at 6 months, these data will be compared to the values appropriate for a 6-month-old infant based on the growth charts). However, only development at 4 and 12 months will be reported as study outcomes, results from other time points will be reported in a separate category.

The unweighted univariate regression will be used to compare the crude (unadjusted) RRs for all outcomes. Adjusted methods will incorporate weights estimated using the IPTW method to balance the cohorts with regard to observable covariates (Section 9.11.2.4). A weighted generalized linear model using a binomial family and a log (relative risk) link will be employed to estimate an adjusted relative risk.

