9.11.2.5. Stratified Analyses

Where sample size permits, stratified/subgroup analyses of all outcomes will be conducted that consider the timing of exposure (earliest trimester of exposure), extent of exposure (cumulative dose during pregnancy or relevant exposure window), country, BMI category at conception, maternal age group at conception (<18 years, 18 to 34 years, 35 to 44 years, and 45 to 50 years), and maternal race and ethnicity.

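### For pregnancy losses and preterm birth, stratifying by cumulative dose lets the outcome set the stratum and can create a false inverse dose-response among women who continue dosing

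*Protocol*

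**What the plan says.** Section 9.11.2.5 says that, where sample size permits, "stratified/subgroup analyses of all outcomes will be conducted". The stratifiers include earliest trimester of exposure and "extent of exposure (cumulative dose during pregnancy or relevant exposure window". The section does not say which of the two dose options applies to which outcome.

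Other sections bear on the point:

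- Section 7.2: "Tirzepatide is a once-weekly subcutaneous injection".
- Section 9.11.2: "All outcomes will be analyzed as binary variables".
- Section 9.11.2.2, on SAB and preterm birth: "for these time-to-event outcomes, data will be censored at appropriate time points", namely 20 and 37 gestational weeks. No landmark, dose rate or time-varying dose is mentioned.
- Table 9.7 gives the exposure windows: date of conception (DOC) to 19 6/7 weeks for SAB, DOC to before 37 weeks for preterm birth, and any trimester for stillbirth and induced abortion.
- Section 9.11.2.1 and Table 9.6: malformations are analysed by first-trimester exposure, with live births as the primary denominator and live births plus fetal losses in a secondary analysis.
- Section 9.7.1: "Detailed information on dose, route, frequency, dates/duration of exposure, and indication/reason for use will be collected".

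**The concern.** A subgroup variable should be settled before the outcome can occur. Cumulative dose of a weekly drug is not. It grows with each week of use and stops growing when the pregnancy ends. Counting from conception, a pregnancy lost at 8 gestational weeks has room for about 8 - 2 = 6 weekly injections, and one that reaches 40 weeks has room for about 38. Those are ceilings, not expected contrasts, but they show the direction: early losses are pushed into the low-dose stratum.

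Choosing the relevant exposure window instead does not help for the four outcomes. A loss at 8 weeks closes the SAB window at 8 weeks, and a delivery at 32 weeks closes the preterm window at 32 weeks.

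Earliest trimester of exposure has a related but different problem for SAB. A woman first exposed in the second trimester must have carried the pregnancy through the first, so her stratum contains time in which no loss could have occurred.

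A dose-response pattern is natural evidence to consult in judging whether an association is causal. Here the error runs towards reassurance.

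**Working it through.** **The plan's own figures.** The protocol gives no figure for the dose strata, so there is none to reproduce. The simulation takes its reference risks from Table 9.4: SAB 11.8%, preterm birth 8.47%.

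**Null simulation for SAB.** The drug has no effect, so the true risk ratio is 1. Everything below except the 11.8% and the weekly interval is assumed.

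- End of pregnancy E: with probability 0.118 a SAB at a gestational week uniform over 6-20, otherwise 40 weeks.
- Planned stop S, in weeks after conception: 2 + an exponential time with mean m.
- Dose count = floor(min(S, E - 2)) + 1.
- Risk ratio = SAB risk above the median count divided by SAB risk at or below it.
- Delayed entry, which section 9.13 acknowledges as left truncation: entry week uniform over the stated range, keeping only pregnancies still ongoing at entry.

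| Mean added use m (weeks) | 2 | 4 | 6 | 8 |
|---|---|---|---|---|
| No delayed entry | 1.00 | 0.89 | 0.71 | 0.61 |
| Entry at weeks 6-14 | 1.00 | 0.99 | 0.91 | 0.84 |
| Entry at weeks 9-14 | 1.00 | 1.00 | 1.00 | 0.97 |

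Repeat runs of 2,000,000 pregnancies differ by about 0.01.

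The pattern has a simple reason. The median planned stop is 2 + m × ln 2 weeks after conception. For m = 2 that is 3.4 weeks, or gestational week 5.4, before any simulated loss, so no distortion arises. For m = 8 it is 7.5 weeks, or gestational week 9.5. Losses before then are forced into the low stratum unless late entry has already removed them.

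**Preterm birth under the same stopping model** (births assumed uniform over weeks 28-37): 0.99-1.01 for all four values of m.

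**When use continues late.** A second set of null runs compared top with bottom dose tertiles. Women who stop do so at weeks 4-8, and the dose per injection is either constant or spread evenly over 2.5-15 mg for illustration.

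| Share continuing | Preterm birth, whole-pregnancy dose | Stillbirth |
|---|---|---|
| All | 0.00 (constant) to 0.73 (varying) | 0.11 to 0.50 |
| Half | 0.00 to 0.94 | 0.27 to 0.86 |
| 5% | 0.98-1.00 | 0.99-1.01 |

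In the 5% scenario SAB gave 0.51-0.79 with entry at week 5, and 0.92-1.00 with entry at weeks 6-14 or 9-14.

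**Check of the remedy.** SAB by dose up to week 10, among pregnancies ongoing at week 10, gives 0.99-1.01 in the first model. In the second model, landmarks at week 8 or 10 give 0.96-1.02, and preterm birth by first-trimester dose gives 0.99-1.02. The null is recovered.

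**The case against.** The strongest reply is that the distortion needs conditions the registry may not meet. Section 7.4.3 says patients are advised to stop when pregnancy is recognised. The main analysis is prospective, SAB is restricted to women enrolled before 20 weeks, and many early losses will never be enrolled. If most women stop early and enter at weeks 9-14, almost nothing is left. That stands, and it rules out saying that a false protective pattern will appear. It can appear.

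It does not dispose of the point, because the share who continue is unknown. The feasibility estimate in section 9.9.2 is built on women who do not discontinue:

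- US: 74.4m × 0.397 × 0.008 × 0.15 = 35,444
- Germany: 42.7m × 0.288 × 0.008 × 0.15 = 14,757
- UK: 14.7m × 0.272 × 0.008 × 0.15 = 4,798
- Applying the birth rates: 35,444 × 0.01233 + 14,757 × 0.009 + 4,798 × 0.00805 = 608 a year
- 608 × 0.05 × 10 years = 304, against the stated 305

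The exposure definition, however, also admits a single dose up to 25 days before conception. Both kinds of user may enrol.

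These are also subgroup analyses with nominal p-values for secondary outcomes. Stillbirth strata are unlikely to be usable: 364 × 0.00596 is about 2 events. Section 9.11 leaves details to the statistical analysis plan. Cut points and models can wait for it, but the choice of cumulative dose for all outcomes is already fixed in the protocol.

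A reader might infer three further things that the protocol does not support:

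- That preterm births generally fall into the low-dose stratum. They do so only with dosing deep into pregnancy.
- That women dosed only before conception score zero dose. Section 9.7.5 counts the 25 days before DOC as exposure during pregnancy; only the SAB and preterm windows in Table 9.7 start at DOC.
- That earliest trimester has the identical fault. It does not grow with gestation; its problem is survival to a late first exposure, and section 9.9.1 assumes 90% are exposed in the first trimester, so the late stratum is small.

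**Conclusion.** The point holds in limited form. For SAB, induced abortion, stillbirth and preterm birth, the planned cumulative-dose strata are partly determined by the outcome, and neither the Table 9.7 windows nor the binary analysis corrects this. The consequence is a possible false inverse dose-response, or a masked true one, among women who continue dosing.

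For SAB the size runs from nothing to a null risk ratio of 0.61 without delayed entry, 0.84 with entry at weeks 6-14, and about 0.97 with entry at weeks 9-14. These figures rest on the assumed loss timing, stopping pattern and median split. Preterm birth and stillbirth matter only with late use. Induced abortion was not simulated; the same reasoning applies to it.

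The primary malformation comparison is untouched: it uses first-trimester exposure among live births. The secondary malformation analysis does include early losses, so cumulative first-trimester dose would be cut short there too.

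**What to change.** Amend section 9.11.2.5. For SAB, induced abortion, stillbirth and preterm birth, and for the secondary malformation analysis that includes fetal losses, replace cumulative dose with one of:

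- dose level at or around conception;
- cumulative dose to a fixed landmark, among pregnancies still ongoing at that landmark;
- time-varying dose to date.

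Handle earliest trimester of exposure for SAB by the same landmark or time-varying approach. Keep first-trimester cumulative dose, counted from 25 days before DOC, for the primary malformation analysis among live births.

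The cost is a sentence or two of protocol text and some programming; dose, frequency and dates are already collected (sections 9.7.1 and 9.8). There are trade-offs. A landmark discards events before it, which for SAB may be a material share, and dose level alone says nothing about duration of use.

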9.11.2.6. Supplementary Analyses

Supplementary descriptive analyses of all outcomes will be conducted as specified for the main analysis population but that include pregnant individuals who were excluded from the main analysis population due to:

- Occurrence of the pregnancy outcome prior to enrollment (retrospectively enrolled participants)
- Exposure to a known teratogen or an investigational medication during or prior to pregnancy (teratogen/investigational medication-exposed participants)
- Exposure to other GLP-1 RA therapies during pregnancy or within 5 times the half-life of the drug prior to conception among the tirzepatide exposed cohort
- Treatment with tirzepatide during pregnancy for reasons other than weight management among the tirzepatide-exposed cohort
- Inclusion of a prior pregnancy in the analysis population (subsequent pregnancies)

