9.7.5. Other Variable Definitions and Ascertainment

Per the American College of Obstetricians and Gynecologists (ACOG), gestational age and the EDD should be determined by the obstetric HCP as soon as data are obtained regarding the last menstrual period (LMP), first accurate ultrasound, or both. The ACOG considers ultrasound measurement of the embryo or fetus in the first trimester (up to and including 13^{6/7} gestational weeks) the most accurate method to establish or confirm gestational age and discourages against changing the EDD based on subsequent ultrasounds. Any pregnancy without an ultrasound before 22^{0/7} gestational weeks to confirm or revise the EDD should be considered suboptimally dated. If the pregnancy resulted from assisted reproductive technology (ART), the obstetric HCP should use ART-derived gestational age (e.g., based on age of embryo and date of transfer) to determine EDD. The ACOG further recommends that the best estimate of EDD by the obstetric HCP, rather than estimates based on LMP alone, be used for research purposes.⁷¹

Based on ACOG's recommendations, the registry will collect the EDD from the obstetric HCP, and the HCP will report whether the EDD was calculated based on LMP, ultrasound, or ART data. If ultrasound-based, whether the ultrasound was performed before 14^{0/7}, before 22^{0/7}, or at 22^{0/7} gestational weeks or later will also be recorded. EDD data will be collected on each data collection form throughout pregnancy. If the HCP reports a corrected EDD on subsequent forms that is different from the EDD initially reported, the registry will evaluate whether a correction is appropriate, based on the timing of the correction and the methods used to determine the corrected EDD, and follow-up with the HCP, if needed.

The registry will conform to the ACOG recommendations for determining the 'best' EDD, and EDD will be used to calculate gestational age. Based on the EDD, the following will be calculated:

- First day of LMP, defined as 0^{0/7} gestational week, will be calculated as EDD minus 280 days (40 weeks)

Gestational age will be calculated as the number of weeks elapsed since the first day of LMP:

- Gestational weeks 0^{0/7} to 13^{6/7} will be considered the first trimester
- Gestational weeks 14^{0/7} to 27^{6/7} will be considered the second trimester
- Gestational weeks 28^{0/7} to pregnancy outcome will be considered the third trimester

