9.11.1.3. Prospectively Enrolled Versus Retrospectively Enrolled Participants

The registry will encourage prospective registration; however, retrospective enrollment in the registry will be permitted. A prospectively enrolled participant is defined as a pregnant individual who enrolls or makes initial contact with the registry prior to pregnancy outcome. A retrospectively enrolled participant is defined as a pregnant individual who enrolls or makes initial contact with the registry after the pregnancy outcome (e.g., live birth, stillbirth, SAB, induced abortion) has occurred (up to 12-months after pregnancy outcome).

Retrospectively enrolled participants can introduce bias toward the reporting of more unusual and severe outcomes and are less likely to be representative of the general population than prospectively enrolled participants. Therefore, retrospectively enrolled participants will be excluded from the main analysis population but will be included in supplementary analyses.

Diagnostic prenatal tests (e.g., ultrasound to scan for structural defects at approximately 20 gestational weeks, chorionic villus sampling, and amniocentesis) can determine with high accuracy whether a fetus has a structural or chromosomal abnormality. Therefore, inclusion of individuals who have had diagnostic prenatal testing in the analysis population may introduce bias. To examine this potential bias, a sensitivity analysis that applies a stricter definition of prospective enrollment will be conducted. For this analysis, individuals who enroll or make initial contact with the registry prior to diagnostic prenatal testing (and pregnancy outcome) will be considered prospectively enrolled, and individuals who enroll or make initial contact with the registry after diagnostic prenatal testing, regardless of the results, will be considered retrospectively enrolled in addition to individuals who enroll after pregnancy outcome. In this sensitivity analysis, the outcomes of individuals who enroll prior to diagnostic prenatal testing will be compared with those of individuals who enrolled after diagnostic prenatal testing.

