Stillbirth [Exposure: Any trimester]	Individuals with pregnancy ending in stillbirth	Individuals included in the analysis population
Sensitivity analysis: Stillbirth	Stillbirths among individuals with pregnancy outcome data	Individuals with pregnancy outcome data
Infant Outcomes		
Minor congenital malformations [Exposure: Any Trimester]	Live births with minor congenital malformations among individuals with pregnancy outcome data	Live births among individuals with pregnancy outcome data
Preterm birth [Exposure: DOC to < 37 weeks gestation]	Singleton preterm live births without MCMs among individuals with pregnancy outcome data who are enrolled (and exposed, if applicable) prior to 37 gestational weeks	Singleton live births without MCMs among individuals with pregnancy outcome data who are enrolled (and exposed, if applicable) prior to 37 gestational weeks

Outcome [Exposure window]	Numerator	Denominator
SGA [Exposure: Any trimester]	Singleton live births who are SGA at birth among individuals with pregnancy outcome data	Singleton live births among individuals with pregnancy outcome data
Sensitivity analysis: SGA	Singleton live births without MCMs who are SGA at birth among individuals with pregnancy outcome data	Singleton live births without MCMs with weight data among individuals with pregnancy outcome data
Postnatal growth and development outcomes		
Postnatal growth deficiency (at 4 and 12 months) [Exposure: Any trimester]	Singleton infants with postnatal growth deficiency based on weight/length/head circumference among infants with weight/length/head circumference data at the time point	Singleton infants with follow-up data at the time point
Sensitivity analysis: Postnatal growth deficiency (at 4 and 12 months)	Singleton infants without MCMs who were not born preterm or SGA with postnatal growth deficiency based on weight/length/head circumference among infants with weight/length/head circumference data at the time point	Singleton infants without MCMs who were not born preterm or SGA with weight/length/head circumference data at the time point
Infant developmental delay (at 4 and 12 months) [Exposure: Any trimester]	Singleton infants with developmental delay in a particular category among infants with developmental milestone data for the category at the time point	Singleton infants with follow-up data at the time point

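### In the supplementary SAB and preterm-birth results, a retrospectively enrolled woman can qualify only if she has already had an early loss or a preterm birth

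*Protocol*

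**What the plan says.** Four parts of the protocol meet here.

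- **Supplementary analyses (9.11.2.6).** "Supplementary descriptive analyses of all outcomes will be conducted as specified for the main analysis population but that include pregnant individuals who were excluded". Five reasons for exclusion are then listed. The first reason is that the pregnancy outcome came before enrollment. No outcome is exempted.
- **Denominators (9.11.2.2, Table 9.7).** The SAB row is limited to "individuals with pregnancy outcome data who are enrolled (and exposed, if applicable) prior to 20 gestational weeks". The preterm row is limited to "Singleton live births without MCMs among individuals with pregnancy outcome data who are enrolled (and exposed, if applicable) prior to 37 gestational weeks". The text below the table repeats the limit for both outcomes: "prevalence will be calculated among the subset of individuals who are enrolled in the registry prior to 20 and 37 gestational weeks, respectively".
- **Retrospective enrollment** (9.11.1.1.3 in the table of contents, 9.11.1.3 in the body heading). "A retrospectively enrolled participant is defined as a pregnant individual who enrolls or makes initial contact with the registry after the pregnancy outcome", and this is allowed for up to 12 months afterwards.
- **Gestational clock (9.7.5).** "Gestational age will be calculated as the number of weeks elapsed since the first day of LMP".

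Table 9.3 defines SAB as a loss before 20 gestational weeks and preterm birth as a live birth before 37.

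**The concern.** The enrollment limits make sense for women who are pregnant when they enroll: they keep in the denominator those still at risk of the event. A retrospective woman is no longer at risk when she enrolls. For her, the same limit selects on the outcome. It admits her if the pregnancy ended early and bars her if it continued.

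This differs from the bias the protocol already acknowledges, that retrospective reports lean toward unusual and severe outcomes. Under that bias, normal retrospective outcomes still enter and partly offset the cases. In these two rows, the denominator rule itself removes the pregnancies that passed the threshold. At stake is a supplementary safety table in a required post-marketing study, which could show raised SAB or preterm figures for reasons unrelated to any drug.

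**Working it through.** **Step 1: who can qualify.** Let T be gestational age at outcome and E gestational age at enrollment, both in weeks since LMP.

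- Retrospective enrollment means T < E.
- The SAB row requires E < 20, so T < E < 20. The pregnancy ended before 20 weeks, as a SAB or an induced abortion. A retrospective pregnancy that reached 20 weeks has E > 20 and cannot enter.
- The preterm row requires E < 37 and a live birth, so T < E < 37. The infant was born before 37 weeks and is a case by the Table 9.3 definition. A retrospective term birth cannot enter.

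This follows from the protocol's definitions and needs no outside figure.

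**Step 2: direction of the effect.** Take a main population of N with prevalence p, and add m qualifying retrospective women, of whom a share s are cases. The new prevalence is (N·p + m·s)/(N + m), which exceeds p exactly when s > p.

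- Preterm: s = 1, so prevalence rises whenever anyone is added.
- SAB: s can be anything from 0 to 1, because induced abortions count in the denominator and not in the numerator.

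**Step 3: how many could be added.** Section 9.9.1 gives 265/0.9/0.9/0.9 = 363.5, rounded up to 364 per cohort; this reproduces. It assumes that 10% of enrolled women are excluded, with loss to follow-up making up 5%. Reading that as 5 percentage points leaves 364 × 0.05 = 18.2, about 18 women. Those 18 must cover retrospective enrollment, teratogen, investigational-drug or infectious exposure, and subsequent pregnancies together. So 18 is a ceiling. Only those who enroll before week 20 or 37 would qualify, although enrollment stays open for 12 months after the outcome.

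**Step 4: illustration.** The rates are from Table 9.4: SAB 11.8%, preterm birth 8.47%. Assumed main populations are N = 364 × 0.9 = 327.6 women for SAB and N = 265 live births for preterm birth. The values of m and s are assumptions.

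| Added (m) | SAB, s = 0.5 | SAB, s = 1 | Preterm, s = 1 |
|---|---|---|---|
| 5 | 12.4% | 13.1% | 10.2% |
| 10 | 12.9% | 14.4% | 11.8% |
| 18 | 13.8% | 16.4% | 14.3% |

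For example, preterm with m = 18: (265 × 0.0847 + 18)/(265 + 18) = 40.45/283 = 14.3%.

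A lower case: if all 18 were retrospective and had the Table 9.4 rates, there would be 18 × 0.118 = 2.1 SABs and 18 × 0.0847 = 1.5 preterm births. Adding only those cases gives (38.66 + 2.1)/(327.6 + 2.1) = 12.4% for SAB and (22.45 + 1.5)/(265 + 1.5) = 9.0% for preterm birth. In the opposite extreme for SAB, where all 18 added women had induced abortions, prevalence would fall to 38.66/345.6 = 11.2%.

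**The case against.** The strongest answer is that the gestational clock stops at the outcome. Section 9.7.5 ends the third trimester there, so a woman whose pregnancy is over is at no gestational week and cannot have enrolled before week 20 or 37. On that reading no retrospective woman enters either row and no bias arises. This stands as a possible reading, but the protocol does not adopt it for the enrollment limits. It also leaves the addition planned in 9.11.2.6 empty for these two outcomes, so the sections still need reconciling.

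A reader might go further and infer that neither reading yields a valid prevalence, or that the supplementary result would then simply equal the main one. The documents do not support that. With the clock stopped, the rows remain valid, and they can differ from the main result because four other excluded groups are still added.

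A reader might also infer that SAB prevalence is inflated by construction. It is not, since induced abortions enter as non-events.

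It is also fair to say that these analyses are descriptive, that retrospective women are kept out of the main population because of reporting bias, and that section 9.13 promises a descriptive evaluation of each source of bias. This limits the consequence. It does not change a denominator rule that selects on the outcome.

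**Conclusion.** The point holds for the supplementary SAB and preterm-birth results. With gestational age counted from LMP, every retrospective infant added to the preterm row is a case, and no retrospective pregnancy that reached 20 weeks can enter the SAB row. Preterm prevalence rises with any addition. SAB prevalence rises when the SAB share among the added women exceeds the main rate. If the clock stops at the outcome, there is no bias, but nothing is added from this group.

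The size is unknown because the protocol does not state the number of retrospective women. About 18 of 364 per cohort is the most its exclusion assumptions allow, and the number who qualify would probably be smaller. The primary and main analyses are untouched.

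Two stronger inferences are not supported. One is a relative risk of a given size between cohorts. It would need retrospective counts by cohort, which the protocol does not give; equal counts added to equal populations at the same rate leave the ratio at 1.00. The other is that all five excluded groups are pooled in a single table. Section 9.11.2.6 lists the reasons for exclusion and does not say so; how the groups are laid out is a matter for the table shells.

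**What to change.** In section 9.11.2.6, state that retrospectively enrolled women are not added to the SAB and preterm-birth prevalences, the rows whose denominator depends on gestational age at enrollment. State also that their SAB and preterm cases are listed by cohort as counts, without a prevalence. The other excluded groups can be added as planned where their members enrolled before the outcome.

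The cost is one or two sentences and a small change to the table shells, with no new data. The downside is that no SAB or preterm prevalence including retrospective women will be reported.
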